9.1. Study design

9.1.1. Overall Design of the Study

This is a prospective, observational, multi-center, open-label, long term, cohort study (OZAWADE® exposed and OZAWADE® unexposed) designed to collect data on the long-term safety of OZAWADE® treatment. This study will be conducted in OSA patients with EDS whose EDS has not been satisfactorily treated by, or who have not tolerated OSA primary therapy. The study will be conducted by physicians specialized in sleep management such as sleep specialists, pulmonologists, cardiologists, otorhinolaryngologist and neurologists.

[figure not shown]
As an observational study, the assignment of the patient to a particular therapeutic strategy should be decided within the current clinical practice and the decision to prescribe OZAWADE® should necessarily precede and be independent of the decision to enrol the patient into the study. OZAWADE® should be prescribed and used based on the routine clinical practice as well as on the individual situation of each patient, according to the approved SmPC.

During the 2-year enrolment phase, 502 patients are planned to be recruited in four to five countries where OZAWADE® is on the market (*i.e.*, France, Germany, Italy and possibly Netherlands, Belgium or Spain), in approximately 8 to 15 centers per country.

Once eligible patients are enrolled, baseline data should be collected. Data collected in the CRF will correspond to data collected in routine practice in the investigating centers.

Patients will be followed-up up to five years, during which time they should be assessed by their treating participating physicians at 6, 12, 24, 36, 48 and 60 months, to follow routine care schedule.

Study visits, procedure and evaluations are summarized in the study flow (Figure 1) and schedule of assessments below (Table 2).

CPAP: Continuous Positive Airway Pressure; EDS: Excessive Daytime Sleepiness; FU: Follow-up; MAD: Mandibular Advancement Device; OSA: Obstructive Sleep Apnoea.

Figure 1: Study Flow.

PASS Protocol [P21-02/OZAWADE]

OZAWADE

Table 2. Schedule of Assessments

	Procedures ¹ /Visits	Inclusion	FU 6 Months	FU Year 1	FU Year 2	FU Year 3	FU Year 4	FU Year 5	End of study
	Visit window		6M [3-9M[12M [9-18M[24M [18-30M[36M [30-42M[48M [42-54M[60M [54-66M[
	Demography: age, gender	X	ē.						
	Profession / Socio-economic status	Х							
Patient interview	Height², weight	Х	Х	Х	X	X	X	X	Х
nten	Waist circumference	X	х	Х	X	X	X	х	Х

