9.1.2. Primary, secondary and exploratory endpoints

9.1.2.1. Primary endpoint

The primary endpoint will be the occurrence of at least one cardiovascular event (CVE) or one serious drug related adverse event during the five years of follow up for each participating patient.

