9.1.3. Patient discontinuation and study termination

The patients are free to withdraw from the study at any time without prejudice to their drug prescriptions or therapeutic management. In this case, their data will be collected up to the time of withdrawal, with no additional information collected thereafter. The patients have also the right to oppose to the use of their personal data for the purpose of the study without prejudice to future medical care by the participating physician. However, in this case and in the case of withdrawal, any adverse events (AE) will still be

collected/reported and followed-up until resolved or stabilised or until the patient died or is lost to follow-up.

Missing evaluations at one or several time points is not a criterion for patient withdrawal.

A patient may be withdrawn from the study prior to completion in case of patient consent withdrawal and physician's or Sponsor's decision and/or safety reason. If the patient withdraws or is withdrawn, the reason will be collected in the eCRF.

All patients discontinuing OZAWADE® will be maintained in the study until completion of the follow-up period.

The participating physicians may interrupt their participation to the study at any time and will immediately inform Bioprojet Pharma.

Bioprojet Pharma reserves the right, at any time, to discontinue enrolment of additional patients into the study, at any site; or to discontinue the study, for medical or administrative reasons and will inform all study stakeholders.

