9.7.5. Primary Analyses

The main objective of the study is to demonstrate that OZAWADE® supplementation does not increase CV events compared with control (non-inferiority). The following analysis will be conducted:

The annual CV morbidity incidence will be estimated by the occurrence of CVE per patient per year equivalent to the proportion of patients with at least one CVE.

The CV risk is known to be higher for OSA patient with existing CV history, using or not CPAP, and well-known risk factors: diabetes, cholesterol, weight, hypertension, demographics (age, gender), lifestyle (fitness, alcohol use, smoking habits).

A generalized linear mixed model featuring Poisson regression will be based on a post stratification model based on the following fixed covariates or random effects:

- nCVE_b, prior CV history measured by the number of CV events experienced before baseline, expected as the essential predicting covariates;
- Risk factors (RF): diabetes, cholesterol, weight, hypertension, alcohol use, and smoking habits reported at baseline;
- Demographics: gender, age, country, study center
- Matched classes propensity clusters: the treatment will be non-randomized but determined by the investigator, involving an expected imbalance between groups on baseline conditions. The decision of prescribing a given medicine will be assumed on a set of baseline covariates defined in the statistical plan. As too many covariates are expected, finding sufficient exact matches is unfeasible, and the goal of subclassification is to form matched subclasses (clusters), such that in each the distribution of covariates for the treated and control groups are as similar as possible. The propensity score will be used as the scalar distance with a two-stage algorithm starting with the nearest neighbour matching and optimized by a full matching procedure [39, 40, 41].

The final model is:

CVE ~ $nCVE_b + \Sigma_i RF_i + gender + age + trt + \{country\} + Offset (log-exp) + \{center | country\} + \{cluster\}$

The notation Σ_i RF_i covers the above mentioned considered risk factors. The obvious effect of the exposure duration is measured by the offset of its logarithm. The last fixed factor is the treatment (trt) binary effect (0=control, 1=pitolisant). Country, site effect nested within country, and cluster (matched group) effects will be used as random factors (between {}).

Sensitivity Analysis

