Site selection bias: Site involvement is voluntary and the final sample of participating sites may not be representative. This potential bias is inevitable in this type of study and its impact is difficult to evaluate. However, this bias will be minimized by the selection of a balanced number of centers in each participating country and by the fact that a feasibility study is on-going to identify physicians that could be interested in participating in the study. For this reason, refusal of few centers is not expected to have a significant impact on sites representativeness. The number of physicians solicited, having answered, having refused, having accepted, the number of sites initiated as well as the number of active sites will be presented. The reasons for refusal will be described.

Sampling bias: due to the exhaustive nature of the collection of subject data, the number of subjects may not be homogeneous between the sites and sites with a higher potential for recruitment may include more patients than others. However, to limit this bias a feasibility study is on-going to identify physicians that will be able to recruit a certain amount of patients. In addition, only physicians specialized in sleep medicine who receive, in medical consultation, OSA patients with diagnosis of excessive daytime sleepiness and who are likely to treat them with OZAWADE (sleep specialists, pulmonologists, cardiologists, otorhinolaryngologists and neurologists) will be selected.

Attrition bias: Patients lost to follow-up are the main source of attrition bias. Attrition can threaten sample representativeness if the patients lost to follow-up differ from the other patients in their baseline characteristics or in their outcomes. To decrease this bias, the centers will contact patients who did not attend their follow-up visits.

10. Protection of human subjects

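### The primary Poisson model assumes a constant cardiovascular event rate over five years, and neither the primary nor the sensitivity analysis checks this

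*Protocol*

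**What the plan says.** Section 9.7.5 describes the primary analysis: "A generalized linear mixed model featuring Poisson regression will be based on a post stratification model". It then gives a formula, called the final model. Its terms are prior CVE count, risk factors, gender, age, treatment, country, center within country, matched cluster, and an offset. On time it says only: "The obvious effect of the exposure duration is measured by the offset of its logarithm".

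The one sensitivity analysis (end of 9.7.5) adds the time between a patient's first CV event and the start of pitolisant. That covariate describes prior history, not time in the study.

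The primary endpoint (9.1.2.1) is the "occurrence of at least one cardiovascular event (CVE) or one serious drug related adverse event during the five years of follow up". The schedule is the same for both groups: "they should be assessed by their treating participating physicians at 6, 12, 24, 36, 48 and 60 months" (9.1.1). On unequal observation, section 9.1.3 says "All patients discontinuing OZAWADE® will be maintained in the study until completion of the follow-up period", and section 9.9 says "Patients lost to follow-up are the main source of attrition bias". Section 9.7.6 plans a Cox model as a secondary analysis, with each patient's record split into inter-visit time-slices.

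**The concern.** A log-time offset with no period term gives each patient one rate for the whole of follow-up. If the true rate is higher early on, a group with a larger share of early person-time has a higher average rate even when the drug does nothing. None of the listed covariates, random effects or propensity clusters removes this, because none describes time since inclusion.

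The non-inferiority conclusion rests on this model. Shorter observation in controls would lower the ratio and favor OZAWADE; shorter observation in the OZAWADE group would raise it and suggest a false signal. The protocol does not treat the rate as constant elsewhere: section 9.7.6 computes cumulative incidence from an incidence density at each time, and section 9.1.2.2 looks at how CVEs are distributed in time.

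**Working it through.** The plan gives no figure for this point that could be reproduced. Margin, alpha, assumed event rate and drop-out are not visible in the public text of section 9.5 and Appendix 1.

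**Inputs from the protocol**
- Offset only, no period term (9.7.5).
- Five years planned in both groups (9.1.1).
- 195 patients per group, used only for scale (9.9).
- About two years of recruitment plus five of follow-up (Abstract); data collection from Q3/Q4 2024 to Q4 2030/Q1 2031 (Table 1).

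**Assumptions, not in the protocol**
- The year-1 rate is *f* times the later rate, with *f* = 1.5 to 3.
- Exposure duration means observed time at risk.
- The true rate ratio is 1.

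**Step 1. Difference in follow-up.** A group followed for T years (T ≥ 1) has an average rate proportional to (f + T − 1)/T. The model estimates the ratio of these averages. For f = 2 and 4 v 5 years: (5/4)/(6/5) = 1.25/1.20 = 1.042.

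| OZAWADE v control, years | f = 1 | f = 1.5 | f = 2 | f = 3 |
|---|---|---|---|---|
| 5 v 5 | 1.000 | 1.000 | 1.000 | 1.000 |
| 4 v 5 | 1.000 | 1.023 | 1.042 | 1.071 |
| 5 v 4 | 1.000 | 0.978 | 0.960 | 0.933 |
| 3 v 5 | 1.000 | 1.061 | 1.111 | 1.190 |
| 5 v 3 | 1.000 | 0.943 | 0.900 | 0.840 |

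The first row and the f = 1 column show that both conditions are needed. Counting first events over time at risk changes little: at a later rate of 0.06 per year, 4 v 5 years gives 1.040 (f = 2) and 1.068 (f = 3).

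**Step 2. Does a period term remove it?** Poisson models were fitted to simulated data with 300,000 patients per group (simulation standard error about 0.004 to 0.005).

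| Case | Offset only | With period term |
|---|---|---|
| f = 2, 4 v 5 years | 1.047 | 1.006 |
| f = 3, 4 v 5 years | 1.071 | 1.000 |
| f = 3, 3 v 5 years | 1.198 | 1.007 |
| f = 3, 5 v 5 years | 0.995 | 0.995 |

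**Step 3. How could person-time differ between groups?**

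*Differential loss.* If a share d leaves at one year, the average rate is proportional to [f + 4(1 − d)]/[1 + 4(1 − d)]. With 5% of OZAWADE patients and 25% of controls leaving, the ratio is 0.98, 0.97 and 0.94 for f = 1.5, 2 and 3. With 5% v 40% it is 0.96, 0.93 and 0.89.

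*Later starters.* Section 9.3.7.1 records OZAWADE begun at a follow-up visit, and 9.7.5 does not say how such patients are counted. Suppose groups of equal size and 20% of controls starting at one year.
- Censored at the switch: [(f + 4)/5]/[(f + 3.2)/4.2] = 0.98, 0.97, 0.95 for f = 1.5, 2, 3.
- Later time moved to the exposed group: [(f + 4.8)/5.8]/[(f + 3.2)/4.2] = 0.97, 0.95, 0.91.
- Kept in their original group: no effect by this route.

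*Milestones.* The data-collection window is 5.75 to 6.75 years, so patients entering at two years get 3.75 to 4.75 years. Even if one group entered wholly in the first year and the other wholly in the second, the null ratio would be only 1.001 to 1.028 (f = 2) or 1.002 to 1.049 (f = 3).

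**Step 4. Scale.** At 195 per group and an assumed later rate of 0.06 per year, the standard error of the log rate ratio is about 0.16 to 0.21. With an assumed one-sided 2.5% test, the false-acceptance rate at the margin under bias B < 1 is Φ(−1.96 + |ln B|/SE). For B = 0.960 this is about 4%; for B = 0.933 it is about 5 to 6%.

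**The case against.** A reader might infer that the non-inferiority ratio will be biased. The documents do not support that: they state neither a changing rate nor unequal follow-up.

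A reader might infer front-loading from the two visits in year 1. An extra visit does not raise the year-1 count of myocardial infarction, stroke, death or any lasting condition; it only finds some sooner. Blood pressure, and ECG when available, are taken at inclusion, and the hypertension component is worded as new onset. Extra visits could inflate only transient findings, such as an isolated QTcF above 450 ms, and at most double them. If those were 25 to 50% of events (an assumption), f would be 1.25 to 1.5, and 5% v 25% drop-out would give 0.990 to 0.982.

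A reader might also infer that controls leave earlier because they have no prescription to renew. No section says so, and the direction is unknown. Patients who stop OZAWADE stay in follow-up, centers contact those who miss visits (9.9), and adverse events are still collected after withdrawal (9.1.3).

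Finally, the Cox model leaves the baseline hazard free, and a gap between its result and the Poisson result would be a warning. Section 9.7 calls itself a summary, so the unseen SAP may add a check.

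Most of this stands and limits the point to a conditional one. Three things remain. The protocol itself fixes the final model. The Cox analysis is secondary, and no rule covers disagreement between the two. Some early detection is also plausible: the QT component does not require new onset, and a first-event rate tends to fall over time in a cohort of mixed risk. That the shift is smaller than the standard error is only a partial answer, because a systematic shift changes the error rate at the margin (Step 4).

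**Conclusion.** The point holds as a conditional weakness. The primary model assumes a constant CVE rate, and neither the primary nor the sensitivity analysis tests it. Bias needs both a rate that changes over follow-up and person-time distributed differently between the groups, and it can go either way. With f between 1.5 and 3, a one-year follow-up difference gives about 2 to 7%. A two-year difference gives about 6 to 19%, which would require large differential attrition.

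These sizes rest on assumed rates and follow-up. Because the margin is not visible, the effect on the non-inferiority conclusion cannot be judged. They also rest on reading exposure duration as time at risk, which 9.7.5 does not define. If the offset were full follow-up with a yes/no endpoint, 4 v 5 years would give 1.029 at 0.06 per year even with a constant rate.

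**What to change.** In section 9.7.5, split each patient's person-time at the planned visit times (0–6, 6–12, 12–24, 24–36, 36–48 and 48–60 months). Keep the log person-time offset within each interval and add the interval as a fixed factor, leaving the other terms unchanged. State what exposure duration means and how patients who start OZAWADE after inclusion contribute time.

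At minimum, name the Cox model in 9.7.6 as the sensitivity analysis for the constant-rate assumption behind the primary non-inferiority result, and say how disagreement between the two will be interpreted.

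The cost is five extra parameters and a data step close to the inter-visit splitting already planned for the Cox model. If the rate proves constant, little is lost. The change does not correct informative drop-out, which needs its own handling.

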anti	Smoking status ³	X ₃	X ³	X ³	X ₃	X ₃	X ₃	X ₃	X ³
Patie	Alcohol consumption	X	х	Х	X	X	X	X	х
	Physical activity	Х	Х	X	X	X	X	X	Х
	Relevant medical history	X							
	Prior medications (last three months)	X							
	Relevant concomitant medications	X	Х	Х	X	X	X	X	Х
e e	Physical examination	X		Х	X	X	Х	X	х
minati	All Adverse Events including adverse events of special interest ⁴		х	х	х	х	X	x	х
l exa	Blood pressure, heart rate	X	Х	Х	X	X	X	X	X
Medical examination	Biological assessment of less than 12 months (cholesterol, glycemia and triglycedemia)	х		х	х	х	х	х	Х
	ECG brought by the patient when available (QT measure) ⁵	X _e	X ⁶	X ⁶	X _e	Xe	Xe	X _e	X _e

PASS protocol Version 3.0 – 23 NOV 2023

PASS Protocol [P21-02/OZAWADE]

OZAWADE

	Procedures /Visits Visit window		FU 6 Months	FU Year 1	FU Year 2	FU Year 3	FU Year 4	FU Year 5	End of study
			6M [3-9M[12M [9-18M[24M [18-30M[36M [30-42m[48M [42-54[60M [54-66[
OSA and sleep history	OSA and sleep history, duration of sleep	X	X ⁷	Х	х	X	Х	Х	Х
	Apnoea-hypopnea index (AHI) At diagnosis of OSA At follow-up visits (with or without CPAP) ⁸	х	х	х	х	х	x	х	х
	Epworth Sleepiness Scale (ESS)	X	X	Х	Х	Х	Х	Х	Х
	CPAP or alternative (e.g., MAD) and adherence ⁹	Х	х	х	х	х	х	х	X
	Maintenance of wakefulness test (MWT) or Multiple Sleep Latency Test (MSLT)	X		х	х	X	х	х	X
	Beck Depression Inventory	Х		Х	Х	Х	Х	Х	Х
	Fatigue Severity scale	X		Х	Х	Х	Х	X	Х
	Assessment of perceived sleepiness at driving	X		х	х	х	х	х	X
OZAWADE* use	Prescription (when applicable)	X							
	Adherence with the Morisky Medication Adherence Scale 8-item (MMAS-8)		х	х	х	х	х	x	х

- 1. Data collected in the CRF will correspond to data collected in routine practice in the investigating centers.
- Height at inclusion visit only.
- 3. Smoking status: in pack-year.
- 4. Adverse events of special interest include the following cardiovascular events: acute myocardial infarction, new onset of angina, unstable angina, stroke (ischemic, haemorrhagic), transient ischemic attack, new onset atrial fibrillation, unscheduled interventional cardiology procedure (stenting, CABG), new onset hypertension (with new hypertension treatment or a posology adjustment of hypertension treatment), new onset or worsening of peripheral vascular disease or unscheduled intervention, stent thrombosis, heart failure, QT prolongation and cardiovascular death.
- 5. ECG when available.
- 6. Last test available at the time of the visit.
- 7. Duration of sleep.

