9.3.7. Exposure and adherence to OZAWADE®

9.3.7.1. Treatment exposure

Exposure to OZAWADE® will be collected at inclusion and at follow-up visits (if not started at inclusion), with the date of prescription and the prescribed dose.

At each follow-up visit, dose modifications, treatment interruptions and permanent discontinuation will be collected. Reasons of changes will also be collected.

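### The primary non-inferiority model has one yes/no OZAWADE term and no analysis by actual exposure, so switching over five years can dilute an on-drug cardiovascular risk toward no difference

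*Protocol*

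**What the plan says.** Section 9.7.5 of the protocol states the aim: "The main objective of the study is to demonstrate that OZAWADE® supplementation does not increase CV events compared with control (non-inferiority". It then gives the final model in full. The treatment enters once: "The last fixed factor is the treatment (trt) binary effect (0=control, 1=pitolisant". Follow-up enters through a single offset: "The obvious effect of the exposure duration is measured by the offset of its logarithm". Patients are grouped into matched clusters by a propensity score built on baseline covariates.

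Elsewhere the protocol provides for exposure that changes over time:

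- Section 9.1.3: "All patients discontinuing OZAWADE® will be maintained in the study until completion of the follow-up period".
- Section 9.3.7.1, on starts: "Exposure to OZAWADE® will be collected at inclusion and at follow-up visits (if not started at inclusion), with the date of prescription".
- Section 9.3.7.1, on changes: "At each follow-up visit, dose modifications, treatment interruptions and permanent discontinuation will be collected".
- Section 9.1.2.1 defines the primary endpoint over the whole five years, whatever happens to treatment.

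The one sensitivity analysis in 9.7.5 adds a covariate for the duration of cardiovascular history. It does not concern exposure. In Table 2 (section 9.1.1) the row "Prescription (when applicable") is ticked at inclusion only, although 9.3.7.1 collects exposure at follow-up visits too.

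**The concern.** The protocol foresees stopping and later starting and collects both, but its final model gives neither a place. It does not say which label a late starter carries, or whether time after stopping remains pitolisant time.

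With one label per patient and an offset equal to follow-up time, off-drug years count as exposed and a late starter's on-drug years count as control. Both move the two groups' rates closer together. In a superiority comparison that costs power. In a non-inferiority safety comparison it helps the claim, so an increase in risk could be missed because of ordinary discontinuation and late starting.

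Coding late starters as exposed from inclusion would not solve this. It would place under pitolisant the time a patient had to live through before the first prescription, which is immortal time and lowers the exposed rate artificially.

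**Working it through.** **Plan's own figure.** There is none to reproduce on this point. The visible text gives no OZAWADE persistence, late-start rate, control event rate or margin; the sample-size text is not available. The values of d, s, RR, event rate, margin and alpha below are therefore assumptions.

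**Inputs from the protocol.** One 0/1 treatment term and one log offset (9.7.5); discontinuers kept in follow-up (9.1.3); late starts, interruptions and stops recorded (9.3.7.1); five-year endpoint (9.1.2.1); 195 patients per group (9.9).

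**Step 1: the label-based ratio.** Let d be the off-drug share of exposed-label person-time, s the on-drug share of control-label person-time, and RR the true on-drug rate ratio. With constant rates, risk raised only while on drug, and switching unrelated to cardiovascular risk:

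observed ratio = [(1 − d)·RR + d] / [(1 − s) + s·RR]

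| d | s | true RR 2.0 | true RR 1.5 |
|---|---|---|---|
| 0.2 | 0.05 | 1.80/1.05 = 1.71 | 1.40/1.025 = 1.37 |
| 0.3 | 0.10 | 1.70/1.10 = 1.55 | 1.35/1.05 = 1.29 |
| 0.5 | 0.20 | 1.50/1.20 = 1.25 | 1.25/1.10 = 1.14 |

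**Step 2: how much stopping this represents.** With a constant annual stopping hazard h over five years, the on-drug share is [1 − exp(−5h)]/(5h). For h = 0.10 this is 0.79 (d = 0.21); for h = 0.20 it is 0.63 (d = 0.37).

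**Step 3: effect on the conclusion.** Set the true on-drug ratio equal to an assumed margin M, so that a non-inferiority claim would be wrong. Use a one-sided 0.025 Wald test on the log rate ratio, 195 patients per group, five full years each, and an off-drug event rate of 5% to 10% per year. With E1 and E0 the expected events in the exposed and control labels, SE = √(1/E1 + 1/E0), and the chance of claiming non-inferiority is Φ([ln M − ln(observed ratio)]/SE − 1.96).

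Worked case, M = 1.5, d = 0.25, s = 0.10, rate 5%: each group has 195 × 5 = 975 person-years. E1 = 975 × 0.05 × 1.375 = 67.0 and E0 = 975 × 0.05 × 1.05 = 51.2. SE = 0.186 and the observed ratio is 1.31. Φ(0.136/0.186 − 1.96) = 0.11.

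| d | s | M = 1.5 | M = 2.0 |
|---|---|---|---|
| 0 | 0 | 2.5% | 2.5% |
| 0.25 | 0 | 7–10% | 11–18% |
| 0.25 | 0.10 | 11–18% | 26–46% |
| 0.50 | 0.20 | 32–55% | 76–97% |

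Each range runs from the 5% to the 10% event rate. This is a simple two-rate test, not the planned mixed model; it shows direction and order of magnitude only.

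**The case against.** The best answer is that the formula does not literally fix the label over time. In 9.7.5 the word fixed contrasts with the random factors; it describes a fixed effect. That is correct, and the quoted sentence alone does not prove a constant label. One label per patient is still the natural reading, because patients are matched on baseline covariates and are described throughout as belonging to a treatment group.

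A second answer is that the statistical analysis plan will deal with it. Section 9.7 calls itself a summary of principles, and 9.7.3.1 says estimands and intercurrent events may be set out in that plan. This softens the point. But the primary model is already written out as final, and a later plan that used time-updated exposure would depart from it. The secondary Cox model in 9.7.6 allows time-varying covariates but does not name treatment as one.

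A third answer is that analysis by initial treatment decision is a legitimate estimand. It is. Where patients stop because of early cardiovascular signs, it can even be the safer analysis, since it keeps later events in the exposed group. A reader might therefore infer that the time-updated analysis should replace the primary one. The protocol does not support that: on-drug time is open to informative stopping and time-varying confounding, and the matching uses baseline covariates only.

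Two stronger readings also fail:

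- A reader might argue that the log of exposure duration does not exist for never-exposed patients. That requires the offset to be time on drug, whereas the dilution requires it to be follow-up time. Since one offset serves both groups, observation time is the sensible reading. The wording still needs settling: with time on drug as the offset for exposed patients and all events counted, a true ratio of 1.0 would appear as 1/0.75 = 1.33 when 75% of their time is on drug, away from no difference.
- A reader might call controls' use of other wake-promoting agents exposure misclassification. The comparator is defined as patients not exposed to OZAWADE (8.1), so it is not.

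**Conclusion.** The point holds as a gap in the primary analysis. The protocol anticipates and records changes in exposure, counts events over five years, and names no analysis by actual exposure for a non-inferiority claim. On the natural reading, an on-drug excess is diluted toward 1, the anti-conservative direction.

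That direction is conditional. It rests on risk being mainly present on drug, switching not being strongly driven by cardiovascular risk, and an offset equal to follow-up time. It would be too strong to say that the bias always runs toward no difference.

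The size is unknown. A true 2.0 appearing as 1.71 or 1.55 follows from assumed shares; the documents cannot show whether the real effect would be trivial or large. Nor does 9.3.7.1 show that crossover is expected to be common. It only provides for recording a start that did not occur at inclusion.

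**What to change.** In section 9.7.5:

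1. State that the offset is the log of person-time at risk.
2. State that the treatment term in the label-based analysis is the treatment decision at inclusion, so that late starters are not coded as exposed from inclusion.
3. Add a co-reported analysis of the primary endpoint. Split each patient's follow-up at the recorded OZAWADE start and stop dates, let treatment be time-updated with a carry-over window stated in advance, and use the person-time of each interval as the offset. Late starters then contribute control time before their start.
4. Claim non-inferiority only if both analyses support it.

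Also reconcile the prescription row of Table 2 with 9.3.7.1 for the follow-up visits.

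The cost is protocol and analysis-plan wording, one table row and one further model. Section 9.3.7.1 already collects the prescription date, interruptions and permanent discontinuation. The downside is that the time-updated analysis can be distorted by informative stopping and time-varying confounding, which is why neither analysis should stand alone. Requiring both makes the claim slightly harder to meet.

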The estimates of the main endpoint will be compared among OZAWADE® users and non-users by a generalized Linear Model featuring Poisson regression. In this model we consider a post stratification model based on fixed covariates combined with a random effect attempting a correction on the expected imbalance due to the non-randomized treatment. Cumulative incidence estimate and Cox proportional Hazard regression will be used as secondary analysis.

Milestones

• Ethics submission: Q2/Q3 2024

Start of data collection: Q3/Q4 2024

• End of data collection: Q4 2030/Q1 2031

• Interim study report: yearly throughout the study

Final report of study results: Q4 2031

5. Amendments and updates

None.

6. Milestones

The planned study milestones, as per Good Pharmacovigilance Practices definitions, are summarized below.

Table 1. Study Milestones

Study Milestone	Planned date
Ethics submission	Q2/Q3 2024
Start of data collection	Q3/Q4 2024
End of data collection	Q4 2030/Q1 2031
Interim study report	Yearly throughout the study
Final report of study results	Q4 2031

7. Rationale and background

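### The matched propensity clusters enter the primary Poisson model only as a random intercept, which gives partial protection against confounding by propensity covariates that are not also fixed terms

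*Protocol*

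**What the plan says.** Protocol Section 9.7.5 expects channelling: "the treatment will be non-randomized but determined by the investigator, involving an expected imbalance between groups on baseline conditions". Its answer is to form matched subclasses, "such that in each the distribution of covariates for the treated and control groups are as similar as possible". On construction it says: "The propensity score will be used as the scalar distance with a two-stage algorithm starting with the nearest neighbour matching", followed by full matching. The covariates of the score are left to the SAP: "The decision of prescribing a given medicine will be assumed on a set of baseline covariates defined in the statistical plan".

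The role of the subclasses is not left open. The section writes out the final model and states: "Country, site effect nested within country, and cluster (matched group) effects will be used as random factors (between" curly brackets). The abstract (Section 4, Statistical Method) gives the purpose: "a random effect attempting a correction on the expected imbalance due to the non-randomized treatment".

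The same model has fixed terms for "prior CV history measured by the number of CV events experienced before baseline, expected as the essential predicting covariates", for "Risk factors (RF): diabetes, cholesterol, weight, hypertension, alcohol use, and smoking habits reported at baseline", and for gender, age and treatment. Section 9.7.5 also names CPAP use and fitness as cardiovascular risk factors, but neither is a fixed term.

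The propensity score has no other route into the planned analyses. Section 9.7.5 gives no matching weights, conditional likelihood, strata or fixed score term. Its one sensitivity analysis adds the time since the first cardiovascular event. In the Cox model of Section 9.7.6 the cluster term serves the robust variance.

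**The concern.** A random intercept is valid for the treatment coefficient if the cluster effect is independent of treatment given the fixed terms. These clusters are built on the probability of treatment. If the score contains a prognostic covariate that the fixed terms omit, a cluster's share treated and its underlying risk move together, and the assumption fails.

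Shrinkage makes this visible. A set with few events says little about its own level, so its estimated effect is pulled towards zero. Part of the difference between clusters is then not absorbed and goes into the treatment coefficient. The balance that matching creates within sets is only partly used.

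At stake is the primary non-inferiority comparison of a safety study without randomisation, in which this term is the stated correction for non-random prescribing.

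**Working it through.** The plan gives no figure on this point. The sample-size inputs (Section 9.5, Appendix 1) are not visible in the copy at hand, so event rates and confounding strengths had to be assumed.

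**From the protocol.** 502 patients (Section 9.1.1); five years of follow-up (Section 9.1.2.1); propensity distance with full matching; Poisson model with log-exposure offset and random cluster intercept (Section 9.7.5).

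**Assumed.** True rate ratio 1; about 1:1 treatment; event rate 0.05 or 0.10 per patient-year; four confounders, each with log-rate slope 0.5 per SD; log-odds slope of treatment 0, 0.25 or 0.5 per SD; no restriction on set size; no country or centre effects.

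**Models.** For patient i in matched set s, with fixed covariates x:

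- Planned: log E(Y) = log(exposure) + β·trt + γ′x + u_s, with u_s ~ N(0, σ²) taken as independent of trt.
- Alternatives with the same x: conditional Poisson within sets; full-matching weights; the planned model plus the linear propensity score as a fixed term.

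Share of bias left = mean estimated log rate ratio ÷ mean crude log rate ratio, since the true log rate ratio is 0.

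**Set size.** Unconstrained full matching gave 129 to 143 sets, so 502/143 = 3.5 to 502/129 = 3.9 patients per set. With five full years that is 3.5 × 5 × 0.05 = 0.9 to 3.9 × 5 × 0.10 = 2.0 expected events per set, so shrinkage is to be expected.

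**Results** (100 replicates per row):

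| Channelling runs through | Rate/yr | Crude RR | Fixed covariates only: left | Planned model: left (RR) | Conditional on sets | Weights | Planned + fixed score |
|---|---|---|---|---|---|---|---|
| fixed terms only | 0.05 | 1.58 | 3% | 4% (1.02) | 3% | 7% | 3% |
| fixed terms only | 0.10 | 1.52 | −4% | −2% (0.99) | −3% | −1% | −4% |
| mostly fixed terms, some outside | 0.05 | 1.95 | 39% | 35% (1.27) | 6% | 6% | 2% |
| mostly fixed terms, some outside | 0.10 | 1.90 | 36% | 28% (1.20) | 3% | 4% | −1% |
| half and half | 0.05 | 2.31 | 56% | 44% (1.44) | 6% | 7% | 3% |
| half and half | 0.10 | 2.30 | 55% | 35% (1.34) | 4% | 7% | 2% |
| outside only | 0.05 | 1.62 | 103% | 72% (1.41) | 5% | 13% | 8% |
| outside only | 0.10 | 1.55 | 100% | 53% (1.26) | 1% | 4% | −1% |

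Example, half and half at 0.05: 0.368/0.838 = 44% for the planned model; 0.023/0.838 = 3% with the score added as a fixed term.

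The Monte Carlo standard error is about 0.02 on the log rate ratio. Against crude values of 0.42 to 0.84 that is 0.02/0.84 = 2 to 0.02/0.42 = 5 percentage points.

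**Precision.** The SD of the estimate is the Monte Carlo standard error × √100. Planned model 0.17–0.25; with fixed score 0.15–0.24; conditional 0.20–0.29; weights 0.21–0.31.

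**The case against.** The strongest reply is that the cluster term is not the model's only defence. The predictor the protocol calls essential, six risk factors, age and gender are fixed terms, and they remove the confounding they carry: the first two rows leave −2% to 4%. A reader might infer that the plan leaves most of the channelling bias in the treatment effect. The documents do not support that. In the simulations it happened only when all channelling ran through covariates outside the model.

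A reader might also infer a bias towards a false non-inferiority claim, reasoning that the cautions on cardiac disease and hypertension (Sections 7.1 and 9.3.3) steer lower-risk patients to the drug. But prior cardiovascular events and hypertension are fixed terms, so that route is already adjusted for. Nothing shows which way CPAP use or fitness would act on prescribing. The upward bias in the table was an input.

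Two further points are fair. The score's covariates are for the SAP, so CPAP use and fitness may not be in it; if they are not, no use of the score would control them. And the protocol states no number or size of subclasses; larger ones would be shrunk less.

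What stands is that the way the clusters enter the model is fixed in the protocol, not deferred. If the score repeats the fixed covariates, the cluster term is nearly redundant. If it holds more, the term adjusts for the extra covariates only partly: in the mixed rows it moved the share left from 36–56% to 28–44%.

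**Conclusion.** The point holds in a limited form. As written, the random cluster term is a weak carrier of the propensity information, and confounding by score covariates that are not also fixed terms is only partly removed. The simulated residual was 28–44% of the crude log rate-ratio bias in the mixed cases and 53–72% when all channelling lay outside the fixed terms, against about −4% to 13% across the three alternatives.

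These percentages rest on assumed event rates, confounding strengths and unrestricted full matching, with country and centre effects left out. They illustrate the mechanism and do not forecast this study's bias. The planned model left more bias than the alternatives in every scenario where confounding ran outside the fixed terms. The sign of any real bias is unknown.

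**What to change.** In Section 9.7.5 keep the Poisson model, its offset and all fixed covariates. Carry the propensity information as a fixed logit-propensity-score term or as propensity strata; conditioning on the matched sets or using full-matching weights would also serve. Do not rely on the random cluster term for this purpose. Use a variance robust to matched set, and report one of the other propensity adjustments as a sensitivity analysis. Align the sentence in the abstract.

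The cost is one line of the model and a little more analysis work. It needs no new patients and no new data. A fixed score term cost no precision in the simulations; conditioning or weights cost a little.

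The change controls only what the score contains, so the SAP's covariate list should be checked for CPAP use and fitness.
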